3 INVESTIGATIONAL PLAN

3.1 Study Design

This is an unmasked, pragmatic randomized controlled trial.

Women randomized to arm 1 will be started on amlodipine 2.5 mg daily. Women randomized to arm 2 will be started on nifedipine ER 30 mg daily. Dose adjustments will be made as deemed appropriate by the clinical team. Intravenous magnesium, additional long-acting antihypertensives, and short-acting antihypertensives will be administered as deemed appropriate by the clinical team. Women will be discharged from the hospital when the team feels that all discharge criteria have been met. While each provider may use slightly different discharge criteria based on their practice patterns, it is agreed upon that no patient will be discharged until her blood pressure is $< 160/110$ mmHg. They will be scheduled for a blood pressure check (virtual or in-person) ideally 3 to 7 days after discharge and an in-person visit ideally at 4 to 6 weeks postpartum. Participation in the study will not affect usual management aside from medication assignment.

3.2 Allocation to Treatment Groups and Blinding (if applicable)

A computer-generated randomization schedule with 1:1 allocation will be utilized.

Randomization will occur at time of study enrollment utilizing REDCap. Randomization will be stratified by chronic hypertension diagnosis status. The research staff will be responsible for accessing the centralized randomization system, obtaining patient allocation, and notifying the treatment team of patient assignment.

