- Need for antihypertensive therapy, defined as blood pressure $>/= 150$ mmHg systolic and/or 100 mmHg diastolic on two occasions four hours apart, or one severe blood pressure >160 mmHg systolic and/or 110 mmHg diastolic.
- Age 18 years or older

Exclusion criteria

- Use of antihypertensives prior to delivery (either for hypertension or other indications, i.e. tachycardia)
- Allergy to nifedipine ER or amlodipine
- Persistent tachycardia (as defined by the treatment team)

Number of Subjects 160

Study Duration Each subject's participation is expected to last less than 8 weeks
The entire study is expected to last 24 months

Study phases

- Screening: Women admitted to Greenville Memorial Hospital Family Birthplace will be screened on admission to determine if they have a hypertension diagnosis. Additionally, postpartum women on the Women's Specialty unit who do not meet criteria prior to delivery will be rescreened once daily. Women with hypertensive diagnoses will be approached about their willingness to participate in the study, either at the time of admission or at time of diagnosis.
- Randomization: Participants will be randomized to either nifedipine ER or amlodipine at the time of enrollment. In order to maximize participant capture, all screened patients who have a hypertensive diagnosis and agree to study participation will be consented and randomized. Only those who progress to needing antihypertensives will meet full inclusion criteria and ultimately be enrolled in the study.
- Intervention: Those participants meeting inclusion criteria for antihypertensives will be administered the study medication. Participants will be administered either amlodipine or nifedipine ER, depending on their treatment arm allocation.

-Follow-up: Data regarding the patient's need for additional medications, side effects, and length of stay will be collected throughout the hospitalization. Patients will attend a blood pressure check visit ideally 3 to 7 days after hospital discharge (virtual (for patients with home blood pressure cuff only) or in-person) and a postpartum visit ideally 4-6 weeks after delivery (in person), per standard of care. Additional data will be collected at these visits.

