2 STUDY OBJECTIVE

2.1 Primary Objective

The primary hypothesis of this study is that amlodipine is noninferior to nifedipine ER in the management of postpartum hypertension, as evidenced by length of stay from delivery until hospital discharge. A noninferiority limit of 24 hours was selected as a clinically relevant difference.

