3.3 Study Duration, Enrollment, and Number of Subjects

Study duration for each participant will last less than 8 weeks (enrollment during initial hospitalization through postpartum visit). 160 patients will be enrolled. This is anticipated to take approximately 18 months.

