4.1 Screening procedure

Women will initially be screened for study participation at the time of admission to Greenville Memorial Hospital's Family Birthplace unit. Additionally, women who do not initially meet criteria will be rescreened daily for the development of a new hypertension diagnosis. Women will be consented for enrollment and randomized at the time of admission or at time of diagnosis to ensure maximum trial participation. Not all women who are initially consented will meet criteria for final inclusion in the study and initiation of the study drug. Based on review of historical data, approximately 50% of patients who meet diagnostic criteria will eventually meet criteria for medication administration.

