6 STATISTICAL CONSIDERATION

6.1 Sample size calculation

An initial power calculation was performed using a standard deviation of 55.2 hours and a non-inferiority limit of 24 hours; to achieve 80% power with a 2-tailed alpha of 0.05, 66 women would be needed in each arm.

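### Does the double use of the word enrolled leave the trial with only about 80 analysed women?

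*Combined protocol and SAP*

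**What the plan says.** The protocol uses the word in two senses.

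- **At randomisation.** Section 3.2: "Randomization will occur at time of study enrollment utilizing REDCap". Section 4.2 also treats randomisation and enrolment as one event, completed before treatment is needed. One sentence of the synopsis (Study phases, Randomization) does the same. Section 4.1 comes close: "Women will be consented for enrollment and randomized at the time of admission or at time of diagnosis".
- **On needing treatment.** The same synopsis bullet ends: "Only those who progress to needing antihypertensives will meet full inclusion criteria and ultimately be enrolled in the study".

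The target is stated in Section 3.3 as "160 patients will be enrolled", and in the synopsis as 160 subjects. Neither place says at which of the two moments a woman is counted. Section 4.1 adds that "approximately 50% of patients who meet diagnostic criteria will eventually meet criteria for medication administration". Section 6.1 gives the requirement: "to achieve 80% power with a 2-tailed alpha of 0.05, 66 women would be needed in each arm". It does not explain the step from 132 to 160, and no section names an analysis population.

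**The concern.** Randomisation comes before the event that makes a woman eligible for drug, so the moment of counting matters. On the protocol's own 50% figure, the two senses differ by a factor of two: 160 treated women (about 320 randomised), or 160 randomised women (about 80 treated). The operational sections, 3.2 and 4.2, carry the randomisation sense, and research staff would have those sections open when using REDCap. If recruitment closed at 160 randomisations and only treated women were analysed, each arm would hold about 40 women against the 66 in Section 6.1. A noninferiority trial of that size could well fail to show noninferiority even if the two drugs gave identical lengths of stay.

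**Working it through.** **Inputs.** Margin 24 h (Section 2.1: "A noninferiority limit of 24 hours was selected as a clinically relevant difference"). SD 55.2 h, 80% power, alpha 0.05 described as two-tailed, 66 per arm (Section 6.1). Allocation 1:1 (Section 3.2). Progression to treatment about 50% (Section 4.1). True difference 0 h is an assumption: Section 6.1 gives none, but the hypothesis at the end of Section 1 is of equal times.

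**Step 1: reproduce the 66.** n per arm = 2 × SD² × (z_alpha + z_power)² / margin².

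- One-sided 0.05: 2 × 55.2² × (1.645 + 0.842)² / 24² = 65.4, so 66. This matches.
- Two-tailed 0.05: 2 × 55.2² × (1.960 + 0.842)² / 24² = 83.0, so 84. This does not match.

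The stated 66 thus rests on one-sided 0.05. That is a separate matter from enrolment, but it means any loss of power must be compared within one alpha.

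**Step 2: power under each count.** Power = Φ(24 / (55.2 × √(2/n)) − z), with z = 1.645 or 1.960.

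| Women per arm | Meaning | 24 / (55.2 × √(2/n)) | One-sided 0.05 | Two-tailed 0.05 |
|---|---|---|---|---|
| 66 | Section 6.1 requirement | 2.498 | 80.3% | 70.5% |
| 80 | 160 treated | 2.750 | 86.5% | 78.5% |
| 40 | 160 randomised, 50% treated | 1.944 | 61.8% | 49.4% |

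If progression were 40% or 60% (an assumed range), 160 randomised women would give 32 or 48 per arm. Power would be 53.8% or 68.6% at one-sided 0.05, and 41.3% or 56.7% at two-tailed 0.05.

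**Step 3: which count fits the protocol's own numbers?**

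- 160 treated: 160 − 132 = 28 women to spare, or 28/160 = 17.5%. At 50% progression this needs 160/0.5 = 320 randomised.
- 160 randomised: 160 × 0.5 = 80 treated, which is 52 short of 132. To reach 132, progression would have to be 132/160 = 82.5%, against the 50% in Section 4.1.

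**Step 4: which count fits the text?**

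- The one sentence that sets randomised women against enrolled women, in the synopsis, reserves enrolment for those who come to need drug.
- Need for antihypertensive therapy, with its blood pressure thresholds, is an inclusion criterion in the synopsis. A woman who has not met it is not yet a full study subject.
- Section 3.4 describes the study population as women in whom antihypertensives have to be started.
- Section 4.1, straight after the sentence on consent and randomisation, says that some consented women will not reach final inclusion. Being consented for enrolment is therefore not the same as being included.

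**The case for a change.** The strongest case for a change is that Sections 3.2 and 4.2 say plainly that enrolment is the moment of randomisation, that 160 is the only recruitment figure given, and that one sentence would remove the doubt at almost no cost. It would also bring into view the roughly 320 consents that the treated count implies within the 18 months of Section 3.3. The inconsistency stands as described, and the power at 40 per arm is correct.

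Three things limit its force.

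- The figure of about 80 analysed women needs two conditions: that the 160 is counted at randomisation, and that only treated women are analysed. The second is not written anywhere. If all randomised women were analysed, that count would give 160 analysed. About half of them would never have needed study drug, which would dilute any difference between the arms. That would be a different problem from a shortfall in numbers.
- Setting 49% against the planned 80% combines this ambiguity with the alpha mismatch in Section 6.1. At two-tailed 0.05 even the full 66 per arm gives only 70.5%.
- The obvious rewording, 160 analysed with 80 in each arm, would not be right either. Section 6.1 assumes 132, not 160. Treatment need arises after randomisation, so the treated women need not split evenly.

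The study-flow figure in Section 4 is not visible in the text available. It may label the steps, so it cannot be used for either side.

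**Conclusion.** This is a terminology slip, not a shortfall in the design. The synopsis sentence, the treatment-need criterion, Section 3.4, the remark on final inclusion in Section 4.1 and the 132 women required by Section 6.1 all support counting the 160 as women who meet the treatment criterion. On that count the plan exceeds its own requirement by 28 women. Power with 80 per arm is 86.5% at one-sided 0.05, the level that reproduces the 66. It is 78.5% at two-tailed 0.05, and that small deficit comes from the alpha statement, not from enrolment.

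The fall to 61.8% (from 80.3%), or to 49.4% (from 70.5%), arises only if staff adopt the count that the authors' own 50% figure makes unworkable and only treated women are analysed. A team that wrote both the 50% and the 66 per arm can be expected to count treated women without being told. Tidier wording would only confirm that and would alter no analysis or result. These figures assume a true difference of zero, the stated SD and a normal approximation. For the planned rank-sum test on normal data they fall only slightly, to about 60% and 48% at 40 per arm.

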Safety Evaluations	While hospitalized, patients will be monitored daily by the clinical team to assess for side effects and ensure adequate blood pressure control. Adjustments will be made by the clinical team as indicated based on patient status. After hospital discharge, patients will be able to call the office with any concerns and additional appointments for evaluation can be made as necessary.
Statistical and Analytic Plan	Noninferiority of amlodipine will be assessed with Wilcoxon Rank-Sum

Data and Safety Monitoring Plan	Participants will be provided with contact information for the PI should they have any concerns.
--	--

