3.4 Study Population

English and Spanish-speaking postpartum women, who delivered at or beyond 20 weeks' gestation, with a diagnosis of chronic hypertension, gestational hypertension, or preeclampsia requiring initiation of antihypertensives.

Exclusion criteria: Use of antihypertensives antepartum, allergy to nifedipine or amlodipine, persistent tachycardia (as defined by treatment team).

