5 STUDY EVALUATIONS AND MEASUREMENTS

-Demographic characteristics and clinical data will be abstracted from the medical chart

-Maternal age

-Gestational age at delivery

-Race

-BMI

-Parity

-Mode of delivery

-Hypertensive diagnosis

-History of diabetes (gestational or pre-gestational)

-Length of stay from delivery until discharge

-Number of acute antihypertensive treatments

-Number of dose increases of initial study drug

-Number of additional long-acting antihypertensives started

-Magnesium use

-Side effects reported

-Medication discontinuation

-Discharging physician

-Blood pressure at blood pressure check appointment

-Blood pressure at postpartum visit

- Readmissions from time of discharge until postpartum visit
- Breastfeeding status at time of postpartum visit
- Patient-reported length of breastfeeding
- Patient-reported breastfeeding satisfaction

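### Randomization is stratified by chronic hypertension, but the named primary test does not use the strata: a cheap, low-priority improvement, not an error

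*Combined protocol and SAP*

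**What the plan says.** Section 3.2 describes the allocation in two statements: "A computer-generated randomization schedule with 1:1 allocation will be utilized", and "Randomization will be stratified by chronic hypertension diagnosis status". It mentions no blocks.

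The one statement about the primary analysis is in the Protocol Synopsis, in the Statistical and Analytic Plan row: "Noninferiority of amlodipine will be assessed with Wilcoxon Rank-Sum". Section 6 contains only the sample size calculation. No section mentions a stratified test, a covariate or an adjusted model.

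Four other statements bear on the point:
- Section 3.3: "160 patients will be enrolled".
- Section 3.4 lists "Use of antihypertensives antepartum" among the exclusions.
- Section 4.1 expects that "approximately 50% of patients who meet diagnostic criteria will eventually meet criteria for medication administration".
- Section 5 lists "Hypertensive diagnosis" among the items abstracted from the chart.

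**The concern.** The plan singles out one factor to control at randomization and then names a test that ignores it. When a stratification factor predicts the outcome, a test within strata removes the between-stratum variation from the comparison. An analysis that pools the strata leaves that variation in.

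Stratified allocation does not by itself ensure balance among the women analysed here. No blocking is described, and only about half of the diagnosed women are expected to reach study drug. Some chance imbalance in chronic hypertension between the arms is therefore likely, and a stratified test would absorb it.

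What is at stake is a little precision, and agreement between the primary comparison and the groups within which the trial randomizes.

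**Working it through.** **Inputs from the documents.** SD 55.2 h, margin 24 h, 80% power and 66 per arm (section 6.1); 160 women (section 3.3), read here as the number analysed, 80 per arm.

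**Inputs assumed.** The share p of women with chronic hypertension and the difference d in mean stay between strata are not given. I use p = 10-30% and d = 12-24 h. The background rates in section 1 (chronic hypertension 0.9-1.5%, preeclampsia 2-8%) would give 0.9/8.9 = 10% to 1.5/3.5 = 43%. Gestational hypertension and the exclusion of antepartum antihypertensive users both push the share down. At 10% the stratum is 16 of 160 women.

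**The plan's own figure.** n per arm = 2 × 55.2² × (z_alpha + 0.8416)² / 24².
- One-sided 0.025, which is what a two-tailed 0.05 implies: 83.04, so 84.
- One-sided 0.05: 65.41, so 66.

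Section 6.1 gives "80% power with a 2-tailed alpha of 0.05, 66 women would be needed in each arm", and the 66 reproduces only at one-sided 0.05. Both readings of alpha are therefore carried forward.

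**Closed form for means.** The share of variance removed is R² = p(1-p)d²/55.2².
- p = 0.1, d = 12: 0.09 × 144 / 3047.04 = 0.43%.
- p = 0.3, d = 24: 0.21 × 576 / 3047.04 = 3.97%.
- Even at p = 0.43, d = 24: 0.2451 × 576 / 3047.04 = 4.6%.

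With 80 per arm the standard error is 55.2 × √(2/80) = 8.73 h, and 24/8.73 = 2.75. Power without stratifying is 78.5% (one-sided 0.025) or 86.5% (one-sided 0.05). Multiplying the standard error by √(1-R²) gives 78.7-80.1% or 86.7-87.7%. The upper ends belong only to the corner p = 0.3, d = 24.

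**Simulation of the rank tests.** Subtract 24 h from each amlodipine stay. Then compare the ordinary rank-sum with the van Elteren statistic, Σ(W_s - E[W_s])/(N_s+1) divided by √(ΣVar(W_s)/(N_s+1)²), where W_s is the amlodipine rank sum in stratum s. There were 40,000 runs per cell; the Monte Carlo standard error of the paired power change is 0.06-0.17 points. Power in %, unstratified / stratified, for normal data, unblocked 1:1 allocation and one-sided 0.025:

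| d | p = 10% | p = 20% | p = 30% |
|---|---|---|---|
| 0 h | 76.1 / 75.6 | 75.8 / 75.4 | 76.3 / 75.6 |
| 12 h | 75.8 / 75.3 | 75.9 / 75.7 | 75.7 / 75.6 |
| 24 h | 75.9 / 76.0 | 76.2 / 76.9 | 75.8 / 76.9 |

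Change in power in points, at p = 10, 20, 30% (taken before rounding):

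| Allocation and one-sided alpha | d = 12 h | d = 24 h |
|---|---|---|
| Unblocked, 0.025 | -0.5, -0.2, -0.1 | +0.1, +0.8, +1.2 |
| Unblocked, 0.05 | -0.2, -0.2, -0.2 | +0.2, +0.7, +1.1 |
| Blocks of 4 among 320, random half reach drug, 0.025 | -0.3, -0.1, -0.1 | +0.4, +0.8, +1.2 |
| Exact within-stratum balance, 0.025 | -0.1, +0.1, +0.2 | +0.3, +0.9, +1.2 |

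**If the stratum has no effect.** Unblocked allocation loses 0.3-0.7 points over both alphas; a separate run of 12,000 per cell gave 0.6-0.8. With exact balance the loss is 0-0.3.

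**Type I error at nominal 2.5%, d = 12-24 h.** Unstratified: 2.40-2.58% unblocked, 2.40-2.59% blocked with half reaching drug, 2.34-2.43% with exact balance. Stratified: 2.37-2.62% over all three. The Monte Carlo standard error is 0.08.

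**Skewed stay.** With an assumed lognormal stay (mean 70 h outside the chronic stratum), unblocked at one-sided 0.025, unstratified power is 96.1-98.0% and the change is 0.0 to +1.3 points.

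**Chance imbalance.** At p = 20% with unblocked allocation, the between-arm difference in share has SD √(2 × 0.2 × 0.8/80) = 0.063. With d = 24 h that moves the comparison by 0.063 × 24 = 1.5 h. This is random variation that the unstratified test already allows for.

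**The case against.** The strongest reply is that the plan is sound as it stands. The ordinary test is valid, the benefit rests on a stratum share and effect that the documents never give, and the sign of the power change is undetermined within the assumed range. With unblocked allocation, every 12 h cell in the table is a small loss. A gain near one point needs a stratum difference as large as the whole margin and a 20-30% share. Gains of about 2 to 6 points appear only at 48 h, which is twice the margin and 0.87 SD, and should carry no weight. The more important gap is that the rank-sum is not tied to the 24 h margin; all the power figures above compare margin-shifted tests that the protocol does not state.

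All of this stands, and it is why the point is rated low. It does not remove the mismatch between how the trial randomizes and how it is said to be analysed, which costs very little to close.

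A reader might infer that leaving out the strata biases the comparison or produces false noninferiority claims. The documents do not support this: in the simulations the unstratified error rate is nominal or slightly below.

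A reader might also infer that stratifying would restore 80% power, because the closed form reaches 80.1% in one corner. For the rank test that same corner goes only from 75.8% to 76.9%. At one-sided 0.05, the alpha that reproduces 66 per arm, 160 women already exceed 80% in the closed form.

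**Conclusion.** The mismatch is real: allocation uses chronic hypertension status and the stated primary test does not. It is an optional, low-priority improvement, not an error in the plan.

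Assuming 160 analysed women, a total SD of 55.2 h, normal data and shares of 10-30%, stratifying changes power by roughly -0.5 to +0.2 points at a 12 h stratum difference and by 0 to about +1.2 at 24 h. If chronic hypertension does not predict stay, the loss is about 0.3-0.8 points unblocked or 0-0.3 with exact balance. Results at one-sided 0.05 were available for unblocked allocation only. The case for the change is that the analysis would follow the randomization; the expected gain in power is too small to be the reason.

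**What to change.** State that the primary noninferiority comparison is stratified by chronic hypertension status as recorded at randomization. Either of two forms will do:
- a van Elteren test after subtracting 24 h from each amlodipine stay; or
- a stratified Hodges-Lehmann difference, amlodipine minus nifedipine ER, whose upper confidence limit at the planned alpha must be below 24 h.

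If the limit is found by inverting the shifted van Elteren test, the two forms give the same decision. A van Elteren test without the shift would not test the margin.

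Make the change in the edit that states how the 24 h margin enters the rank test, since that wording is needed with or without stratification. The cost is one or two sentences, with no new data and no extra patients: the stratum is fixed at randomization, and the diagnosis is already abstracted. It is not wholly free, because a few tenths of a point of power may be lost if the stratum is not prognostic.

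### The arm can be known before final inclusion is settled, and no stated rule fixes who is analysed

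*Combined protocol and SAP*

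**What the plan says.** Section 4.1 puts randomization before the need for treatment is known: "Women will be consented for enrollment and randomized at the time of admission or at time of diagnosis to ensure maximum trial participation". It adds that "Not all women who are initially consented will meet criteria for final inclusion in the study and initiation of the study drug", and expects that "approximately 50% of patients who meet diagnostic criteria will eventually meet criteria for medication administration". The Protocol Synopsis (Randomization) agrees: "Only those who progress to needing antihypertensives will meet full inclusion criteria and ultimately be enrolled in the study". Section 3.2, however, uses enrollment for the moment of randomization, so the word has two meanings in the protocol.

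Sections 3.1 and 4.2 say that the trial is not masked. Under Section 3.2, research staff are responsible for "obtaining patient allocation, and notifying the treatment team of patient assignment", with no time given. Section 4.2 gives the reason for randomizing early: treatment should not wait for an allocation. It also refers to a study flow figure, which is not shown in the text available for this review.

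The Synopsis defines treatment need by numeric blood pressure thresholds. One exclusion reads "Persistent tachycardia (as defined by the treatment team", and Section 3.4 repeats it. Another is "Use of antihypertensives prior to delivery (either for hypertension or other indications, i.e. tachycardia".

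On analysis, the Synopsis says "Noninferiority of amlodipine will be assessed with Wilcoxon Rank-Sum". Section 6 holds only the sample size calculation. Neither names an analysis set.

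**The concern.** Randomization protects a comparison only for the set of women fixed by it, or by facts that the arm cannot influence. Here about half of those randomized are expected to leave before treatment, and the team that may already know the arm has a part in deciding who enters. If an exclusion, or a decision not to start study drug, depends on the arm, the women compared are no longer a fair split.

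Such a shift in length of stay could go either way. In a noninferiority trial the harmful direction is the one that makes amlodipine look shorter, because it raises the chance of a false noninferiority claim. It would arise if longer-stay women were lost from the amlodipine arm, or shorter-stay women from the nifedipine ER arm. The outcome gives no independent protection: Section 3.1 leaves discharge to unmasked providers whose criteria may differ slightly.

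**Working it through.** **Which entry decisions are open once the arm can be known**

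- *Blood pressure criterion:* settled after randomization, but numeric and recorded. Little room for judgment.
- *Persistent tachycardia:* defined by the treatment team, which is also told the arm. It can emerge after randomization. This is the main opening.
- *Antihypertensive use before delivery:* a charted fact. It is still open only for women randomized before delivery, so it is a lesser concern.
- *Allergy:* essentially a baseline fact.
- *Not starting study drug, or exclusion after disclosure:* no rule says whether the woman stays in the comparison.

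**The plan's own figure.** Section 6.1 uses SD 55.2 h, limit 24 h, 80% power and a 2-tailed alpha of 0.05, and states 66 per arm. With n = 2 × [55.2 × (z_alpha + 0.842) / 24]²:

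- z = 1.960 (one-sided 0.025, matching 2-tailed 0.05): 83.04, so 84 per arm.
- z = 1.645 (one-sided 0.05): 65.4, so 66 per arm.

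The stated 66 is reproduced only at one-sided 0.05. The point made here does not depend on that, but it means the level has to be named in the illustration below.

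**Illustration of tolerance.** Assumptions not in the documents: the 160 of Section 3.3 are qualifying women, 80 per arm; the true difference is exactly 24 h; women are lost selectively from one arm only, all in the direction that favours amlodipine; stays are normal with SD 55.2 h.

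- SE = 55.2 × √(2/80) = 8.73 h.
- Shift that doubles 2.5% to 5% = (1.960 − 1.645) × 8.73 = 2.75 h.
- If a fraction f of an arm is lost and those women differ from the retained by d, the retained mean shifts by f × d.
- False noninferiority = 1 − Φ(1.960 − shift/SE), with SE = 55.2 × √(1/80 + 1/(80 − k)) after k losses.

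| Lost from one arm | d | Shift | False noninferiority (one-sided 0.025) |
|---|---|---|---|
| 0 of 80 | – | 0 | 2.5% |
| 2 of 80 | 27.6 h (0.5 SD) | 0.69 h | 3.0% |
| 2 of 80 | 55.2 h (1 SD) | 1.38 h | 3.57% |
| 4 of 80 | 27.6 h (0.5 SD) | 1.38 h | 3.56% |
| 4 of 80 | 55 h (about 1 SD) | 2.75 h | 4.96% |
| 8 of 80 | 27.5 h (about 0.5 SD) | 2.75 h | 4.91% |

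Simulation with the Wilcoxon test that the plan names (40,000 runs, after subtracting 24 h) gives 2.4% with no loss, 3.5% for 2 of 80 at 1 SD, 5.2% for 4 of 80 at 1 SD and 4.7% for 8 of 80 at 0.5 SD. At one-sided 0.05, doubling 5% needs a shift of 3.17 h, and the case of 4 of 80 at about 1 SD gives 9.1%.

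**Would the losses be visible?** At 50% progression, 160 qualifying women imply about 160/0.5 = 320 randomized, 160 per arm. The number of starters in one arm then varies by chance with SD 4.48, and 80/160 against 76/160 gives Fisher p = 0.74. Counts of starters alone would not show a loss of 4. A table of exclusions by arm and reason does better: 8 against 0 of 160 gives p = 0.007. For 4 against 0, p = 0.12, which is not significant but can be seen in the table.

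**The case against.** The strongest reply is that much of this is read from silence. Section 3.2 gives no time for the notice, so it fits disclosure at qualification as well as at randomization. No section says that exclusions are judged after allocation; staff may apply them at screening, and the missing figure may show this. The one gate that the protocol clearly places after randomization is numeric. Antihypertensive use before delivery is a matter of record, and arm-related bias there would require a team to change care before delivery because of the drug assigned for afterwards. Section 3.1 says usual management is otherwise unaffected. Both drugs are of one class, and no reason is given why tachycardia would be called differently by arm. The Synopsis and Section 3.4 already point to a set of randomized women who qualify. The calculation needs several losses in one direction with the true difference exactly at the limit.

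Most of this stands as a limit on size. It does not remove the gap. Silence on timing is not a safeguard, persistent tachycardia can declare itself after screening, and a description of who is enrolled does not say that those women are analysed by assigned arm, whether or not they start.

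A reader might infer more: that the trial will be biased, that early randomization is itself a flaw, that both exclusions are equally open to judgment, or that selective losses would be too few to notice. The documents support none of these. They show no arm-related exclusion, early randomization has a sound stated reason, use before delivery is a charted fact, and a tabulation by reason would expose the larger losses.

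**Conclusion.** The concern holds in a limited form. As written, entry to the primary comparison is settled after the arm can be known, one exclusion rests on the judgment of the team told the arm, and no stated rule keeps a woman in the comparison by assigned arm. The room for selection is small because the main gate is numeric.

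The size of any bias cannot be derived from the documents. The rise from 2.5% to about 3.6% to 5.0% is a tolerance, not a forecast. It rests on 80 qualifying women per arm, SD 55.2 h, one-sided 0.025, a true difference at the 24 h limit, and 2 to 4 of 80 women lost selectively at about 1 SD. With smaller or mixed losses the effect is less.

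The change should be made because it is cheap and alters both conduct and analysis. Confidence is medium, since the timing of disclosure and of the exclusion checks is inferred and the flow figure was not available.

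**What to change.** Keep early consent and early REDCap randomization.

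1. **Analysis set.** Define the primary set as all randomized women who meet the recorded numeric blood pressure criterion and have no exclusion recorded before the arm was disclosed. Analyse them by assigned arm, whether or not study drug is started.
2. **Reporting.** Tabulate randomized women who do not enter the set, by arm and reason.
3. **Disclosure.** Where it causes no treatment delay, have research staff release the arm to the treatment team only once qualification and the exclusion check are recorded, and log the time.
4. **If the arm must be released earlier.** Record tachycardia status before release. Women given antihypertensives between release and delivery would then stay in the primary set, so add a sensitivity analysis without women who received antihypertensives before delivery.

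Items 1 and 2 need a short amendment and a record of reasons and times. Item 3 costs a logged step per woman at the very point that Section 4.2 tried to clear. The documents do not show off-hours cover by research staff, so it may not be feasible at all hours; items 1, 2 and 4 still apply in that case.
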